### 5.3.2 Technical Factors

Only photon (x-ray) beams with photon energies 4-15 MV or electron beams with electron energies of 6-12 MeV will be allowed.

### 5.3.3 Localization, Simulation, and Immobilization

Patients will be positioned in a stable position capable of allowing accurate reproducibility of the target position from treatment to treatment. Patient immobilization must be reliable enough to ensure that the gross tumor volume (GTV) does not deviate beyond the confines of the PTV as with any significant probability (i.e., < 5%). Patients will undergo an imaging study (electron portal imaging, conebeam computed tomography or Megavoltage computed

tomography) immediately prior to treatment to ensure proper alignment of the geometric center (i.e., isocenter) of the simulated fields.

### **5.3.4 Target Volumes**

#### **5.3.4.1 Image Acquisition**

Computed tomography will be used for targeting and treatment planning. IV contrast is encouraged when its use will enhance target delineation but is not required. Axial acquisitions with gantry 0 degrees will be required with spacing  $\leq 3.0$  mm between scans in the region of the tumor.

#### **5.3.4.2 Target Volume**

The treatment lesion will be outlined and designated the gross tumor volume (GTV). No additional clinical target volume (CTV) margin for microscopic spread will be added. Depending on the stability and reproducibility of patient setup an additional margin of 0.5 – 3 cm will be added to the GTV to constitute the PTV.

#### **5.3.4.3 Technique and Dose Calculations**

Conformal treatment approaches including 3D conformal radiotherapy using static, preferably non-coplanar fields; intensity modulated radiotherapy (IMRT), Volume Modulated Arc therapy (VMAT), Dynamic Conformal Arc Radiation Therapy (DCART), and helical tomotherapy are acceptable. Isodose lines covering the PTV must be  $\geq 95\%$  of the prescribed dose. When IV and/or oral contrast are used, contrast densities should be overridden in the planning process. Tissue density heterogeneity correction is required for lung tumors. Superposition/convolution dose algorithms are preferred.

All radiotherapy plans will be centrally reviewed by [name] prior to delivery of the first fraction.

### **5.3.5 Organs at Risk**

#### **5.3.5.1 Defining Organs at Risk**

Palliative radiotherapy is delivered as standard of care to a subcutaneous, nodal, or visceral treatment lesion. The anatomic location of the treatment lesion is undefined and left to the discretion of the treating physician. Therefore, a designated set of organs at risk to be included in each radiotherapy treatment plan cannot be defined. Organs at risk will be defined by the treating radiation oncologist if visible within the axial slices covered by the PTV. Organs at risk to be contoured include but are not limited to: optic nerves, globes, cochlea, brainstem, spinal cord, cauda equina, sacral plexus, esophagus, brachial plexus, heart, great vessels, trachea and proximal bronchial tree, rib, skin, stomach, duodenum, jejunum/ileum, colon, rectum, bladder, penile bulb, femoral heads, renal hilum, lungs, liver, and kidneys. These contours should be

labeled according Standard Naming Conventions listed below in parentheses as per <https://www.rtog.org/CoreLab/StandardizedNamingConventions.aspx>. Organs at risk should be defined using existing guidelines and atlases available at:

<https://www.rtog.org/CoreLab/ContouringAtlases.aspx>. If necessary, the assistance of a board certified radiologist should be sought to aid in contouring. Guidelines for defining commonly encountered organs at risk are described below.

- Spinal cord (Spinalcord): The spinal cord will be contoured based on the bony limits of the spinal canal. The spinal cord should be contoured starting at least 10 cm above the superior extent of the PTV and continuing on every CT slice to at least 10 below the inferior extent of the PTV.

- Brachial plexus (BrachialPlex\_L and BrachialPlex\_R): The defined ipsilateral brachial plexus originates from the spinal nerves exiting the neuroforamina on the involved side from around C5 to T2. However, for the purposes of this protocol, only the major trunks of the brachial plexus will be contoured using the subclavian and axillary vessels as a surrogate for identifying the location of the brachial plexus. This neurovascular complex will be contoured starting proximally at the bifurcation of the brachiocephalic trunk into the jugular/subclavian veins (or carotid/subclavian arteries) and following along the route of the subclavian vein to the axillary vein ending after the neurovascular structures cross the second rib.

- Esophagus (Esophagus): The esophagus will be contoured using mediastinal windowing on CT to correspond to the mucosal, submucosa, and all muscular layers out to the fatty adventitia. The esophagus should be contoured starting at least 10 cm above the superior extent of the PTV and continuing on every CT slice to at least 10 below the inferior extent of the PTV and ideally from the post-cricoid space to the GE junction.

- Great Vessels (GreatVessels): The great vessels (aorta and vena cava, not the pulmonary artery or vein) will be contoured using mediastinal windowing on CT to correspond to the vascular wall and all muscular layers out to the fatty adventitia. The great vessel should be contoured starting at least 10 cm above the superior extent of the PTV and continuing on every CT slice to at least 10 cm below the inferior extent of the PTV. For right sided tumors, the vena cava will be contoured, and for left sided tumors, the aorta will be contoured.

- Heart/pericardium (Heart): The heart will be contoured along with the pericardial sac. The superior aspect (or base) for purposes of contouring will begin at the level of the inferior aspect of the aortic arch (aortopulmonary window) and extend inferiorly to the apex of the heart.

- Trachea and proximal bronchial tree (Trachea, BronchialTree): The trachea and proximal bronchial tree including the mainstem and lobar bronchi including trachea, the carina, the right and left mainstem bronchi, the right and left upper lobe bronchi, the intermedius bronchus, the right middle lobe bronchus, the lingular bronchus, and the right and left lower lobe bronchito the bifurcation of the first segmental airways will be contoured using mediastinal windows on CT to

correspond to the mucosal, submucosa and cartilage rings and airway channels associated with these structures.

- Skin (SkinOAR): The skin will be defined as the outer 0.5 cm of the body surface. As such it is a ring of uniform thickness (0.5 cm) which envelopes the entire body in the axial planes. The cranial and caudal surface of the superior and inferior limits of the planning CT should not be contoured as skin unless skin is actually present in these locations (e.g., the scalp on the top of the head).

- Stomach (Stomach): The entire stomach and its contents should be contoured as a single structure as a continuation of the esophagus and ending at the first part of the duodenum.

- Duodenum (Duodenum): The wall and contents of the 1st, 2nd, and 3rd parts of the duodenum will be contoured as one structure beginning where the stomach ends and finishing as the superior mesenteric artery crosses over the third part of the duodenum

- Jejunum/ileum (Smallbowel): Small bowel from end of duodenum to the ileocecal area.

- Large Bowel (Largebowel): From the ileocecal area to include the ascending, transverse, descending and sigmoid colon as one structure.

- Renal hilum/vascular trunk: The renal artery and vein from the renal cortex to the great vessels.

- Liver (Liver): The entire liver minus the GTV

- Kidneys (Kidney\_L and Kidney\_R): Both the right and left kidney, excluding renal pelvis/collecting system, should be contoured in their entirety (the renal cortex)

- Lung (Lungs): Both the right and left lungs should be contoured as one structure. Contouring should be carried out using pulmonary windows. All inflated and collapsed lung should be contoured; however, gross tumor (GTV) and trachea/ipsilateral bronchus as defined above should not be included in this structure.

- Rectum: The muscular wall of the rectum should be contoured, extending from the anus to the rectosigmoid junction

- Femoral Heads: The right and left femoral heads extending to the lesser trochanter should be contoured separately

- Bladder: Outer muscular wall should be contoured

### 5.3.5.2 Organs at Risk Dose Constraints

Listed below are the maximum dose limits to a point or critical volume within organs at risk. Maximum point dose will be defined as the maximum dose to a 0.035 cc volume. These are absolute limits, and treatment delivery that exceeds these limits will constitute a major protocol violation. As outlined above other organs at risk may be defined by the treating physician based on the location of the treatment lesion and these organs should be constrained using standard accepted dose constraints. Radiotherapy will be delivered as 24 Gy over 3 fractions of 8 Gy, 20 Gy delivered over 5 fractions of 4 Gy, or 4 Gy delivered over 2 fractions of 2 Gy and the constraints will vary based on the prescribed dose. In all cases the maximum hotspot for a given plan should not exceed 120% of the prescribed dose. For 4 Gy delivered over 2 fractions of 2 Gy there are no dose constraints for organs at risk.

For 20 Gy delivered over 5 fractions of 4 Gy dose constraint for the optic nerves, globes, cochlea, brainstem, and spinal cord is a max point dose of 22 Gy (4.4 Gy / fx). For the lung (right and left) 1500cc should receive less than 12.5 Gy. For the liver 700cc should receive less than 15 Gy. For the kidneys (right and left) 200cc should receive less than 15 Gy. All other organs at risk should be constrained to below 120% of the prescribed dose.

For 24 Gy delivered over 3 fractions of 8 Gy the dose constraints for organs at risk are listed in the Table 3. Recent studies have shown that the rib and chest wall in proximity to the treated lesion may represent an organ at risk for complication such as chest wall pain and rib fracture. While target coverage should not be compromised to limit dose to the rib/chest wall and formal constraint is not provided, every effort should be made to minimize dose and hotspots to this organ at risk.

Table 3. Critical Organs at Risk Dose-Volume Limits for 24 Gy over 3 fractions

Structure	Volume (mL)	Volume Max (Gy)	Max Point Dose (Gy)	Volumetric Constraint
Optic nerves			15	
Globes			15	
Cochlea			18	
Brainstem			18	
Spinal cord	<0.25	17	18	
Sacral Plexus	<5	21.9	24	
Brachial plexus	<3	20.4	24	

Cauda equina	<5	21.9	24	
Esophagus	<5	21	27	
Great Vessels	-	-	25.2 (105% of Rx dose)	
Heart/pericardium	<15	24	25.2 (105% of Rx dose)	
Trachea and ipsilateral bronchus	<4	15	25.2 (105% of Rx dose)	
Skin			28.8	
Stomach	<10	21	24	
Duodenum	<5	15	22.2	
Jejunum/ileum	<5	16.2	25.2 (105% of Rx dose)	
Colon/Rectum	<20	24	28.2 (105% of Rx dose)	
Bladder	<15	16.8	28.2	
Renal Hilum	<15	19.5	-	
Femoral Heads	<10	21.9		
Liver	700mL spared from volume max	15		
Kidneys	200mL spared from volume max	14.4		
Lung (left and right)	1500mL spared from volume max	10.5		V20<10%

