**Reporting of Results**

All patients included in the study must be assessed for response to treatment, even if there are major protocol treatment deviations or if they are ineligible. Each patient will be assigned one of the following categories: 1) complete response, 2) partial response, 3) stable disease, 4) progressive disease, 5) early death from malignant disease, 6) early death from toxicity, 7) early death because of other cause, or 8) unknown (not assessable, insufficient data).

All of the patients who met the eligibility criteria should be included in the main analysis of the response rate. Patients in response categories 4-8 should be considered as failing to respond to treatment (disease progression). Thus, an incorrect treatment schedule or drug administration, or failure to complete all prescribed study therapy, does not result in exclusion from the analysis of the response rate. Sub-analyses may then be performed on the basis of a subset of patients, excluding those for whom major protocol deviations have been identified (e.g., early death due to other reasons, early discontinuation of treatment, major protocol violations, etc.). The reasons for excluding patients from the analysis should be clearly reported. There will be a planned analysis of patients who are evaluable for response (see section 12.4) which will be used for the Simon two-stage design.

The 95% confidence intervals should be provided.

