## 12.5 Subject Course

Information regarding the subject's course such as completing the study treatment, dose delays, premature discontinuation and major protocol violation will be tabulated and summarized.

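### Table 3 labels the colon/rectum point-dose limit of 28.2 Gy as 105% of the prescription, but 105% of 24 Gy is 25.2 Gy, so doses between the two pass by the figure and fail by the label

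*Combined protocol and SAP*

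**What the plan says.** Section 5.3.5.2 gives each radiotherapy regimen its own organ limits. The table for the highest-dose regimen is titled "Table 3. Critical Organs at Risk Dose-Volume Limits for 24 Gy over 3 fractions". Its point-dose column is in Gy, and five rows add a percentage of the prescription in brackets:

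- Great vessels, heart/pericardium, trachea and ipsilateral bronchus, and jejunum/ileum each read "25.2 (105% of Rx dose" (bracket closed in the table).
- Colon/rectum reads "28.2 (105% of Rx dose" (likewise).

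The bladder row, directly below colon/rectum, also reads 28.2 Gy but has no percentage.

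On the force of the limits, the section says: "These are absolute limits, and treatment delivery that exceeds these limits will constitute a major protocol violation". It also caps every plan as a whole: "In all cases the maximum hotspot for a given plan should not exceed 120% of the prescribed dose".

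Major violations reappear in two places. Section 12.5 says that "premature discontinuation and major protocol violation will be tabulated and summarized". In Section 10.1, Reporting of Results says: "Sub-analyses may then be performed on the basis of a subset of patients, excluding those for whom major protocol deviations have been identified".

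**The concern.** One cell states two limits for the same organ, and they differ. Because the protocol treats these limits as absolute, the cell decides whether a plan is acceptable and whether a delivered treatment counts as a major violation. For a colon/rectum point dose between the two values, the protocol gives no single answer.

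What is at stake is plan acceptance for bowel dose and the consistent classification of violations. Those classifications feed a descriptive tabulation and optional sub-analyses. The point does not touch the DLT definition, the CTCAE-based safety endpoint, the sample size or the Simon two-stage rules.

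**Working it through.** **Inputs (Section 5.3.5.2 unless noted)**

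- Prescription to which Table 3 applies: 3 x 8 Gy = 24 Gy.
- Colon/rectum maximum point dose: 28.2 Gy, labelled 105% of prescription.
- Four other rows with the same label: 25.2 Gy.
- Whole-plan hotspot cap: 120% of prescription.
- All prescriptions in the protocol (Section 5.3.1): 24, 20 and 4 Gy.

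**Step 1. Reproduce the labelled figures.** Limit = percentage x prescription.

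- 1.05 x 24 = 25.2 Gy. This matches all four other rows exactly.
- It does not match the 28.2 Gy printed for colon/rectum.

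**Step 2. Look for a reading that gives 28.2 Gy.**

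| Reading | Calculation | Result |
|---|---|---|
| 28.2 Gy as a share of 24 Gy | 28.2 / 24 | 117.5% |
| Prescription at which 28.2 Gy would be 105% | 28.2 / 1.05 | 26.9 Gy, not used in this protocol |
| 105% of the 20 Gy regimen | 1.05 x 20 | 21.0 Gy |
| 105% of the 4 Gy regimen | 1.05 x 4 | 4.2 Gy |
| Hotspot cap at 24 Gy | 1.20 x 24 | 28.8 Gy |

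None yields 28.2 Gy. Section 6.6 allows the prescribed radiotherapy dose to be lowered but not raised, so a dose change cannot produce 26.9 Gy.

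**Step 3. Size of the disputed band.**

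- Total: 28.2 - 25.2 = 3.0 Gy, and 3.0 / 25.2 = 11.9% of the lower limit.
- Per fraction: 25.2 / 3 = 8.4 Gy and 28.2 / 3 = 9.4 Gy, a gap of 1.0 Gy.

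**Step 4. Does another rule close the band?**

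- The hotspot cap of 28.8 Gy lies above both values.
- The colon/rectum volume limit allows less than 20 mL above 24 Gy. Both candidate point doses exceed 24 Gy, so this limit does not choose between them.
- The point-dose cell is therefore the operative ceiling for this organ, and it is the cell that conflicts.

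**Step 5. Reach.** Only 8 Gy x 3 plans are affected, though that regimen is open to both cohorts. For 4 Gy x 5 this organ falls under the general limit of 120% of prescription (1.20 x 20 = 24 Gy). For 2 Gy x 2 there are no organ limits.

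**The case against.** The best defence is that the column is headed in Gy, so the number is the limit and the bracket is a mistaken gloss. The table lends this some support. Bladder has 28.2 Gy with no label. Esophagus at 27 Gy (27 / 24 = 112.5%) and skin at 28.8 Gy (28.8 / 24 = 120%) also exceed 105% of prescription, so 28.2 Gy would not be out of place. The label could have been carried down from the jejunum/ileum row just above.

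This is plausible but remains an inference. The four 25.2 Gy rows with the identical label point the other way, and no rule gives the figure precedence. The documents do not settle which half is wrong.

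A second defence is that safeguards make the matter small. Section 5.3.4.3 says: "All radiotherapy plans will be centrally reviewed by" a named reviewer before the first fraction. Section 3 gives bowel as an example of an unsuitable treatment site, so colon or rectum matters only as a neighbour of the target. The main response analysis keeps patients despite incorrect treatment. The documents offer no basis for estimating how often a plan would fall in the band, and no tolerance dose showing that 28.2 Gy is harmful.

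All of that stands, and it limits the weight of the point. Central review can make practice consistent, but the reviewer works from the same contradictory cell and cannot learn from it which limit the protocol sets.

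**Conclusion.** The cell is wrong as written and should be fixed. The figure is 117.5% of the 24 Gy prescription and the label says 105%. The two readings differ by 3.0 Gy in total, or 1.0 Gy per fraction, and a colon/rectum point dose above 25.2 and up to 28.2 Gy passes one and fails the other.

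The arithmetic rests only on Table 3 applying to 24 Gy in 3 fractions, as its title says. No assumption is made about which half was intended. The gap measures an inconsistency in a limit the protocol calls absolute; it is not evidence of bowel toxicity at the higher value. The consequence is confined to plan acceptance and the recording of major violations.

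**What to change.** Amend the colon/rectum point-dose cell of Table 3 in one of two ways, as the radiation oncology lead confirms:

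1. Keep the 105% label and change the figure to 25.2 Gy.
2. Keep 28.2 Gy and either delete the label or change it to 117.5% of prescription.

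Check the unlabelled 28.2 Gy in the bladder row at the same time. Until the amendment is in force, apply 25.2 Gy to colon/rectum, since a plan at or below that dose satisfies both readings.

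The cost is a one-cell correction plus a check of one neighbouring cell. Sample size, schedule and analysis do not change.

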## 6. GENERAL PLAN TO MANAGE SAFETY CONCERNS

Measures will be taken to ensure the safety of patients participating in this trial, including the use of stringent inclusion and exclusion criteria (see Sections 4.1 and 4.2) and close monitoring (as indicated below and in the study calendar).

### 6.1 Eligibility Criteria

Eligibility criteria were selected to guard the safety of patients in this trial. Results from the nonclinical toxicology studies as well as the nonclinical/clinical data from other studies were taken into account.

### 6.2 Monitoring

Safety will be evaluated in this study through the monitoring of all serious and non-serious AEs, defined and graded according to NCI CTCAE v4.03. Patients will be assessed for safety (including laboratory values) according to the Study Calendar. Patients will be followed for safety for 30 days following the last dose of study treatment or until receipt of another anticancer therapy, whichever comes first. General safety assessments will include serial interval histories, physical examinations, and specific laboratory studies, including serum chemistries and blood counts (see Study Calendar for the list and timing of study assessments). **All serious adverse events (SAEs) will be reported in an expedited fashion.** In addition, the investigators will review and evaluate observed AEs on a regular basis.

Patients who have an ongoing study treatment–related AE upon study completion or at discontinuation from the study will be followed until the event has resolved to baseline grade, the event is assessed by the investigator as stable, new anticancer treatment is initiated, the patient is lost to follow-up, the patient withdraws consent, or until it has been determined that study treatment or participation is not the cause of the AE.

### 6.3 Management of Specific Adverse Events

Toxicities associated or possibly associated with protocol treatment should be managed according to standard medical practice. Additional tests, such as autoimmune serology or biopsies, may be used to determine a possible immunogenic etiology.

Although most immune-related adverse events observed with immunomodulatory agents have been mild and self-limiting, such events should be recognized early and treated promptly to avoid potential major complications. Discontinuation of protocol therapy may not have an immediate therapeutic effect and in severe cases, immune-related toxicities may require acute management with topical corticosteroids, systemic corticosteroids, mycophenolate, or TNF- $\alpha$  inhibitors.

#### **6.4 Management of Adverse Events from Immunotherapy**

The primary approach to Grade 1-2 immune-related adverse events is supportive and symptomatic care with continued protocol therapy; for higher grade immune-related adverse events, therapy should be held and oral/parental steroids administered. Recurrent Grade 2 immune-related adverse events may also mandate holding therapy or the use of steroids. In the case of all toxicities consideration for benefit/risk balance should be made by the investigator, with consideration of the totality of information as it pertains to the nature of the toxicity and the degree of clinical benefit a given patient may be experiencing prior to further administration of ERS therapy. ERS therapy should be permanently discontinued in patients with life-threatening immune related AEs (irAE). Management of AE by grade (Table 3) and symptomatic management of specific AEs (Table 4) are outlined below.

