**Table 4. General Management of AE by Grade (refer to Table 4 for specific AEs)**

irAE Toxicity Grade	Withhold/ Discontinue	Action Taken With Respect to Epacadostat	Supportive Care (see also Table 4)
Grade 1	No action.	Not applicable.	Provide symptomatic treatment.
Grade 2	May withhold study treatment per investigator's discretion.	If AE resolves within 30 days, subject may restart at the same dose and schedule for epacadostat. For an AE that does not resolve within 30 days, consider reducing epacadostat 1 dose level.	Consider systemic corticosteroids in addition to appropriate symptomatic treatment.
Grade 3	Withhold study treatment until AE resolves to $\leq$ Grade 2. Discontinue if study treatment cannot be resumed within 30 days.	Restart epacadostat at reduced dose level except in the case of Grade 3 rash that resolves without oral steroids. If AE does not resolve to $<$ Grade 2 within 30 days after re-initiating study treatment or progresses again to grade 3 after initiating study treatment reduce epacadostat 1 dose level. Discontinue therapy for grade 3 pneumonitis.	Systemic corticosteroids are indicated in addition to appropriate symptomatic treatment. May use 1-2 mg/kg prednisone or equivalent per day. Steroid taper should be considered once symptoms improve to $\leq$ Grade 2 and tapered over at least 4 weeks in most cases.
Grade 4	Withhold study treatment until AE resolves to $\leq$ Grade 2. Discontinue if study treatment cannot be resumed within 30 days.	Restart epacadostat at reduced dose level if the AE resolves to $\leq$ Grade 2 or baseline. If there is recurrence of a Grade 3/4 AE with reduced dose of epacadostat, then discontinue participation in the study.	Systemic corticosteroids are indicated in addition to appropriate symptomatic treatment. May use 1-2 mg/kg prednisone or equivalent per day. Steroid taper should be considered once symptoms improve to $\leq$ Grade 2 and tapered over at least 4 weeks in most cases.

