**Table 4: Specific Management of Adverse Events**

Adverse Event	CTCAE v4.03 Grade	Recommended Symptom Specific Management (to be used at discretion of treating physician)
Injection site reaction	1-3	Administer 325-650 mg acetaminophen po every 4-6 hours prn. Note: Maximum cumulative daily dose of acetaminophen is 4 grams daily due to risk of severe liver toxicity.
Injection site reaction	4	Hold study treatment until injection site reaction resolves
Rash	1-2	Supportive care including topical emollients, sun protection, consider topical steroids
Rash	3	Interrupt epacadostat, use topical corticosteroids, consider oral corticosteroids. When rash $\leq$ grade 1, taper steroids if used, then restart at reduced dose. If only topical steroids used, can restart at same or reduced dose when $\leq$ grade 1..
Rash	4	Interrupt epacadostat and start oral steroids. Continue until $\leq$ grade 1 and taper steroids. Once steroids $\leq$ 10mg/day, restart at reduced dose
Flu-like symptoms	1-3	Administer 325-650 mg acetaminophen po every 4-6 hours prn. Note: Maximum cumulative daily dose of acetaminophen is 4 grams daily due to risk of severe liver toxicity.
Headache	1-3	Administer 325-650 mg acetaminophen po every 4-6 hours prn. Note: Maximum cumulative daily dose of acetaminophen is 4 grams daily due to risk of severe liver toxicity.
Nausea/vomiting	1 or 2	Prescribe antiemetics per treating physician's recommendation
Nausea/vomiting	3 or 4	Interrupt study treatment. Prescribe antiemetics per treating physician's recommendation. Fluid and electrolytes should be substituted via IV infusion if indicated. When nausea/vomiting resolves to $\leq$ Grade 2 restart epacadostat at a reduced dose level.
Diarrhea/colitis	1	Subjects should be carefully monitored for signs and symptoms of enterocolitis (such as diarrhea, abdominal pain, blood, or mucus in stool, with or without fever) and of bowel perforation (such as peritoneal signs and ileus). Continue treatment with epacadostat, and initiate supportive care measures, which include drinking liberal quantities of clear fluids. If sufficient oral fluid intake is not feasible, fluid and electrolytes should be substituted via IV infusion. An antidiarrheal can be started.

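### Section 6.4 permanently stops ERS after a life-threatening immune-related event, but the Grade 4 table row directs a reduced-dose restart with no such exclusion, and no text says which rule prevails; two Grade 2 rows leave the 30-day hold limit similarly open.

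*Combined protocol and SAP*

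**What the plan says.** **Stop rule.** Section 6.4: "ERS therapy should be permanently discontinued in patients with life-threatening immune related AEs (irAE"). The same section asks the investigator to weigh benefit against risk before giving more ERS, and then introduces two adverse-event tables. Both are captioned Table 4, although Sections 6.4 and 6.6 call the first one Table 3.

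**General table.** This is captioned "General Management of AE by Grade (refer to Table 4 for specific AEs"), and its rows are irAE grades.
- The Grade 4 row says "Restart epacadostat at reduced dose level if the AE resolves to" Grade 2 or lower, or baseline. It ends treatment only if a Grade 3/4 event recurs at the reduced dose, or under the 30-day rule that it shares with Grade 3: "Discontinue if study treatment cannot be resumed within 30 days".
- The Grade 3 row adds "Discontinue therapy for grade 3 pneumonitis". The Grade 4 row has no matching line.
- The Grade 2 row suggests considering a one-level reduction when an event has not resolved by 30 days.

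**Specific-event table.** Its column is headed "Recommended Symptom Specific Management (to be used at discretion of treating physician").
- Grade 4 rash: once steroids are at or below "10mg/day, restart at reduced dose".
- Grade 3-4 nausea/vomiting: on resolution to at most "Grade 2 restart epacadostat at a reduced dose level".
- Grade 3-4 diarrhea/colitis: reduced-dose restart on return to baseline.
- Grade 2 pneumonitis: return is permitted on improvement to Grade 1 or lower, with 12-week limits for resolution and for steroid reduction.

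**Hold limit.** Sections 6.6 and 6.7 require ERS to end when toxicity keeps epacadostat from being resumed after 30 days. Section 8 lists a toxicity delay of more than 30 days as a reason to stop.

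**The concern.** A site that looks up the Grade 4 row, as Section 6.6 tells it to, could restart epacadostat in a patient whom Section 6.4 takes off ERS for good. Section 2.6 calls the safety of 300 mg BID epacadostat with SD-101 uncertain, so the stop rules should allow one reading only.

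There is also a measurement consequence. Section 6.7 and Table 10 count as treatment intolerance any treatment-related event that requires ERS to be discontinued. Section 6.7 excludes epacadostat dose reductions from that label and reports them separately. Whether a life-threatening irAE counts against tolerability can therefore depend on which rule the site applied.

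The hold limit raises a smaller issue of the same kind: two Grade 2 rows can be read as allowing return to treatment after Sections 6.6, 6.7 and 8 have ended it.

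**Working it through.** The plan gives no figure to reproduce. The check compares the texts and adds a little arithmetic.

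**1. Specific-event rows that reach grade 4, by what they say at first occurrence**

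| Instruction | Rows | Count |
|---|---|---|
| Restart at reduced dose, no life-threatening exclusion | rash 4; diarrhea/colitis 3-4; nausea/vomiting 3-4 (relevant only if judged immune-related) | 3 |
| No stop at first occurrence, no explicit reduced-dose restart | injection-site reaction 4 (hold until resolved); type 1 diabetes 3-4; thyroid 3-4; hepatic 3-4 and renal 3-4 (stop only for persistent grade 4) | 5 |
| Stop outright, in line with Section 6.4 | pneumonitis 3-4; hypophysitis 4; Hy's law | 3 |

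3 + 5 + 3 = 11 rows, of which 3 stop treatment at first occurrence. For an irAE in the middle group, the remaining by-grade instruction is the general Grade 4 row, which says restart.

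**2. Grade 4 pneumonitis.** The specific row stops it. The general Grade 3 row stops grade 3, but the general Grade 4 row is silent and directs a restart. Read alone, the general table is stricter at grade 3 than at grade 4.

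**3. Effect on the tolerability label.** Take a treatment-related, life-threatening irAE after the DLT window that resolves within 30 days.
- Under Section 6.4, ERS must stop, so Section 6.7 and Table 10 count intolerance.
- Under the Grade 4 row, epacadostat restarts one level down, and Section 6.7 does not count a dose reduction.

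The documents give no rate of such events under ERS, so the expected number is unknown. To show scale only, assume the denominator is a completed phase 2 cohort as sized in Section 12.1. One reclassified patient then moves the tolerability percentage by 100 × 1/30 = 3.3 points (solid tumor) or 100 × 1/14 = 7.1 points (lymphoma).

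**4. Inside the DLT window.** Under Section 3, most treatment-related non-hematologic events of grade 3 or higher are DLTs, as are pneumonitis holds over 14 days. Section 8 lists DLT as a reason to stop and Section 6.7 counts it as intolerance, so the gap is smaller there.

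**5. Hold limit.** 12 weeks × 7 = 84 days; 84 − 30 = 54 days. If both clocks start at the last dose, the pneumonitis row leaves Days 31 to 84 open. The general Grade 2 row has no upper limit and covers every Grade 2 irAE. For a patient whose drug is being held, its advice on events unresolved at 30 days can be read as permission to restart at a lower dose.

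**The case against.** **Section 6.4 comes first and the tables govern the rest.** The stop is stated immediately before the tables are introduced, so a careful reader can apply it first and use the Grade 4 row for other events. Both texts can then be obeyed. That reading is available and is probably the intended one, so this is closer to a missing exclusion than to a flat contradiction. What remains is that no sentence says so, the general table is not marked discretionary, and Section 6.6 names the tables as the source of discontinuation criteria.

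**Grade 4 is not the same as life-threatening.** A reader might infer that every Grade 4 instruction contradicts Section 6.4. The documents do not support that: they do not equate the two, and Section 13.3.1 defines life-threatening by immediate risk of death in the investigator's view. The conflict covers only irAEs that meet that definition.

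**Other brakes exist.** Section 6.4 requires a benefit/risk judgement, Section 8 allows a stop for unacceptable events or physician discretion, and Section 6.6 allows phase 1 dose reduction only after the DLT window. These make re-challenge less likely but do not settle which rule applies.

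**The 12-week row does not order anyone past Day 30.** A reader might infer two irreconcilable hold limits. The row is permissive and sits in a discretionary table, whereas Sections 6.6 and 6.7 are mandatory. A site that stops at Day 30 complies with everything. This point largely stands: the 54 days measure an ambiguity, not a direct conflict.

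**Conclusion.** The point holds in bounded form. For life-threatening irAEs, Section 6.4 and the general Grade 4 row lead to opposite actions unless the reader supplies a precedence that the text does not state. Two of the discretionary rows (rash 4, diarrhea/colitis 3-4) repeat the restart, as does a third (nausea/vomiting 3-4) if the event is judged immune-related. After the DLT window this affects patient safety and the classification of the secondary tolerability endpoint.

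A reader might infer that tolerability is untouched because the intolerance label is fixed at 30 days. That is true of the hold-limit issue only. It does not cover the restart issue, where the label depends on whether the event required discontinuation. Nor does anything here change the Simon two-stage design figures.

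The hold-limit issue is secondary and is one of clarity. The conclusion rests on treating the life-threatening irAE as treatment-related and on using the Section 13.3.1 definition. The number of patients affected cannot be estimated from the documents.

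**What to change.** (a) In the general table's Grade 4 row, add: *Permanently discontinue for any life-threatening irAE (Section 6.4; term as defined in Section 13.3.1) and for grade 4 pneumonitis; otherwise restart at reduced dose.*

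(b) In Section 6.4 and above both adverse-event tables, add one sentence: *The life-threatening stop in Section 6.4 and the 30-day maximum hold in Sections 6.6, 6.7 and 8 prevail over every table row, including the general Grade 2 row and the 12-week limits for grade 2 pneumonitis.*

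The precedence sentence covers all 11 specific rows at once, so they need no separate edits and no clinical limit has to be rewritten. If the sponsor in fact wants a longer hold for grade 2 pneumonitis, that should be written as an explicit exception in Sections 6.6, 6.7 and 8; the documents do not show that this was intended.

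The cost is protocol wording, with no added visits or patients. The downside is that a few patients recovering from a grade 2 event after Day 30 could not resume epacadostat, which is what Section 6.6 already says.
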